#### Antitumor Activity of Trametinib in Cancer Other Than Melanoma

In a phase 1/2 monotherapy study, acute myeloid leukemia (AML) or myelodysplastic syndrome (MDS) patients were given trametinib at dose levels from 1-2 mg QD. Drug-related AEs in 45 patients were similar to that observed in patients with solid tumors, and 2 mg PO QD was selected for further investigation in this patient population. Twelve patients (23%) withdrew due to an AE, including cardiac failure (2) and infection (2). Efficacy was reported in 39 patients (Borthakur *et al.*, 2010). The best response in 13 patients with KRAS or NRAS mutations included 3 CRs (23%), 7 SD (54%), and 1 PD (progressive disease) (5%). In 26 patients with wild-type RAS or an unknown mutation, there were 2 PRs (8%).

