
A. [Trametinib]: 2 mg daily of a 28 day cycle  A* Trametinib 1.5 mg daily of a 28 day cycle (when used in combination with GSK2141795)
 
B. [GSK2141795]: 50 mg daily of a 28 day cycle
 
a. Albumin, alkaline phosphatase, total bilirubin, bicarbonate, BUN, calcium, chloride, creatinine, LDH, magnesium, phosphorus, potassium, total protein, SGOT [AST], SGPT [ALT], sodium, fasting serum glucose. Weight and serum creatinine will be used to calculate creatinine clearance (eGFR and eCCR). Also see protocol guidelines for patient management and reporting of elevated liver function tests.
 
b. A single 12-lead ECG should be performed at screening and on the indicated visits. The QT interval corrected for heart rate should be calculated using the Bazett's formula. (<math>QT_c = QT / \sqrt{RR}</math>)
 
c. Myeloma lab tests: <math>\beta</math>2Microglobulin (collected at screening only); serum immunoelectrophoresis, immunoglobulin assay, M band confirmation by immunofixation and quantitation by SPEP, free light chain and 24 hour urine collection for Bence Jones protein to be performed at baseline prior to study, prior to each cycle thereafter and at time of study discontinuation (if last tests were > 4 weeks). FreeLyte test should occur if indicated by the Investigator. Not all tests may be required at each assessment time point. Tests can be done up to 7 days prior to day 1 of each cycle.
 
d. Radiological assessment for clinically suspected extramedullary disease should be performed prior to study (28 days) and every 12 weeks or upon clinical suspicion of progressive disease. This may include CT scan of the abdomen/pelvis, CT or x-ray of the chest, or ultrasound of the liver/spleen or abdomen. To ensure comparability, the baseline radiographs/scans and subsequent radiographs/scans to assess response should be performed preferably using identical techniques. The same method, radiological or physical, should be employed and assessed by the same individual on each occasion if possible.
 
e. Serum pregnancy test (women of childbearing potential).
 
g. Skeletal survey (including skull, all long bones, pelvis and chest) required if previous survey >12 weeks from study entry and at any time when clinically indicated.
 
h. Details on collection of samples, handling and shipping are provided in the Study Lab Manual. The patient may be dosed prior to study visit on cycle 2 day 1 (of single agent trametinib) and cycle 2 day 1 (of combination) to facilitate 2-4 h waiting for bone marrow aspiration. Baseline correlatives can be > 4 weeks prior to start of protocol therapy providing collection is after informed consent.
 
i. Refer to section 5.4
 
j. TSH testing to be done at the beginning of every 4th cycle
 
k. Snellen Chart and Visual Field Testing. If results of visual testing are abnormal the patient will be referred for an urgent full ophthalmologic exam
 
l. The exam will include indirect fundoscopic examination, visual acuity (corrected), visual field examination, tonometry, and direct funduscopy.
 
m. To be performed if available at the treating institution.
									

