In order to be classified as a hematologic response, confirmation of serum monoclonal protein, serum immunoglobulin free light chain (when primary determinant of response) and urine monoclonal protein (when primary determinant of response) results must be made by verification on two consecutive determinations.

- Bone marrow aspirate and biopsy are **only** required to document or confirm CR or sCR, except for patients with evaluable disease **only**, where BM assessment is required to document all response categories including progression. However, a second confirmatory BM is **not** required to confirm response.
- Radiographic studies are not required to satisfy these response requirements, however, if radiographic studies were performed there should be no evidence of progressive or new bone lesions.
- Progression does not require confirmation, but treating physician may continue an additional cycle to confirm progression if clinically indicated.

Bone progression: Caution must be exercised to avoid rating progression or relapse on the basis of variation of radiologic technique alone. Compression fracture does not exclude continued response and may not indicate progression. When progression is based on skeletal disease alone, it should be discussed with the Principal Investigator before removing the patient from the study.

The same method of assessment and the same technique should be used to characterize each identified and reported lesion at baseline and during follow-up. Imaging-based evaluation is preferred to evaluation by clinical examination unless the lesion(s) being followed cannot be imaged but are assessable by clinical exam.

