**The primary objective is** to evaluate the antitumor activity of trametinib determined by overall response rate (ORR), in groups of patients with relapse or refractory multiple myeloma that are:

- Biomarker positive (NRAS, KRAS, BRAF mutated as defined [Appendix F](#))
- Biomarker negative (without NRAS, KRAS, BRAF mutation)

The endpoint for the primary objective, ORR, is evidenced by confirmed response rate, defined as number of patients with partial response or better by IMWG criteria divided by the number of patients in the applicable group (biomarker positive or negative). All patients included in the study will be assessed for response to treatment, even if there are major protocol treatment deviations or if they are ineligible (see section 13.5.2). The patient will be classified as having had a response if he/she has a confirmed response per the definitions in section [11.2.2](#). (i.e., a stringent complete response, or complete response or near complete response or very good partial response or partial response noted as the objective status of two consecutive assessments). The rate of minor response (MR) and progressive disease (PD) will also be observed.

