### 13.2 Sample Size/Accrual Rate

A two-stage design will be used for each group to test the null hypothesis that the extended ORR is 5% or less, versus the alternative hypothesis that the extended ORR is greater than 5% using a one-sided test with a 10% level of significance and 90% power at the alternative extended ORR of 20%. The null hypothesis of extended ORR=0.05 and the alternative extended ORR=0.20 are chosen with reference to response rate with trametinib in BRAF mutated melanoma of 22% (Flaherty *et al.*, 2012) and the response rates of single agent carfilzomib (17%) (Jagannath *et al.*, 2012) and pomalidomide (7%) (Dimopoulos *et al.*, 2012). The design is standard for such single-arm Phase II studies and appropriately minimizes the number of expected study participants when the experimental treatment is truly ineffective.

The target enrollment therefore is a minimum of 24 evaluable subjects and a maximum of 74 if both groups (biomarker positive and biomarker negative) accrue to the second stage. After testing the drug on 12 patients in each group, the trial will go to the second stage if one or more subjects respond. If the trial goes to the second stage, a total of 37 patients will be studied. If the total number of responding is more than or equal to 4, the drug is accepted. The same design as above will apply to both strata. The maximum number of this study would be 74 patients for both strata. The distribution of PFS and DOR will be summarized for each cohort using the Kaplan-Meier method. For each of these endpoints, patients will be right-censored at the date at which they were last known not to have the corresponding event.

Subjects who receive at least one dose of trametinib will be evaluable for safety. AEs will be coded according to the Medical Dictionary for Regulatory Activities (MedDRA) adverse event dictionary. The results will be tabulated to examine their frequency, organ systems affected, and relationship to study treatment. The results of laboratory assessments will be evaluated similarly. Interim safety data will be examined on an ongoing basis to ensure subject safety.

Exploratory analyses of the association of response with pharmacogenomic and pharmacodynamic will be descriptively summarized. Overall, given the limited sample size these analyses will be largely hypothesis-generating.

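### A patient who stops treatment within 4 weeks of a first PR has no required second assessment, so an unconfirmed response scores as a non-response in the primary ORR unless the site chooses to repeat the test

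*Combined protocol and SAP*

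**What the plan says.** **Endpoint.** Section 13.1 defines the primary ORR as a confirmed response rate over all patients in the biomarker group. A response counts if it is a stringent complete, complete or near complete response, "or very good partial response or partial response noted as the objective status of two consecutive assessments". Section 11.2.1 likewise says that monoclonal protein or free light chain (FLC) "results must be made by verification on two consecutive determinations". Neither section sets a minimum interval or requires the patient to be on treatment at the second test.

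**Schedule.** Myeloma assessments are repeated every 4 weeks, and may be drawn up to 7 days before day 1 of each 28-day cycle. The calendar marks a myeloma assessment at Off Study, but the row carries footnote c, which schedules the tests "prior to each cycle thereafter and at time of study discontinuation (if last tests were" more than 4 weeks old). The safety follow-up column, 4 weeks after the last treatment, has no myeloma assessment.

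**Decision rule.** Section 13.2, for each group: "After testing the drug on 12 patients in each group, the trial will go to the second stage if one or more subjects respond". The total is then 37 patients, and the drug is accepted with 4 or more responders. The aim is to "test the null hypothesis that the extended ORR is 5% or less", "using a one-sided test with a 10% level of significance and 90% power at the alternative extended ORR of 20" per cent.

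**Confirmation timing.** The text after the response table in section 11.2.2 allows the two assessments at any time before new therapy. Its list of categories names CR, sCR, VGPR and PD, and leaves out PR.

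**The concern.** A waiver for tests less than 4 weeks old saves redundant sampling in most patients. It does something different for a patient whose last test was the first to show a response. For that patient the off-study sample is the one that decides the primary endpoint, and the waiver removes the requirement just when tests are on schedule.

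The patients affected are those who stop promptly for a reason other than progression. Section 5.3 lists withdrawal and intercurrent illness among the reasons for stopping. Section 6.1 contains triggers for permanent or immediate discontinuation, including grade 4 general toxicity, retinal vein occlusion, the liver stopping criteria, grade 4 pneumonitis and symptomatic LVEF decline. Patients who stop for progression found on testing have had their second assessment and are rightly unconfirmed.

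What is at stake is a downward bias in the observed ORR, under a rule where one patient can close a group. It also makes the endpoint depend on whether a site repeats a test that it need not do.

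**Working it through.** **1. Inputs (section 13.2).** p0 = 0.05, p1 = 0.20, one-sided level 10%, power 90%; n1 = 12, continue with at least 1 responder; n = 37, accept with at least 4.

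**2. Reproduce the design.** The exact acceptance probability is

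A(p) = Σ over x = 1 to 12 of P[Bin(12, p) = x] × P[Bin(25, p) ≥ max(0, 4 − x)].

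At p = 0.20:

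| Stage 1 responders | P(stage 1) | P(enough in the next 25) | Product |
|---|---|---|---|
| 0 | 0.0687 | stop | 0 |
| 1 | 0.2062 | 0.9018 | 0.1859 |
| 2 | 0.2835 | 0.9726 | 0.2757 |
| 3 | 0.2362 | 0.9962 | 0.2353 |
| 4 or more | 0.2054 | 1 | 0.2054 |

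The sum is 0.902. The same formula at p = 0.05 gives 0.0935, below the 10% ceiling. The planned level and power both reproduce.

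**3. Sensitivity to one patient.** At a confirmed ORR of 20%, P(exactly 1 of 12) = 12 × 0.20 × 0.80^11 = 0.206. In about one group in five, the decision to continue would rest on a single responder. Over 37 patients the expected number of responders is 37 × 0.20 = 7.4, so one lost responder is 1/7.4 = 13.5% of them.

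**4. When the waiver applies.** The 4 weeks run from the date of the last draw.
- Draw on day 1: the waiver covers practically the whole cycle.
- Draw on day −7: it lapses at about day 21 to 22, and a later stop in that cycle requires the test.
- Stop after a toxicity hold of 28 days: the last test is normally more than 4 weeks old, so footnote c requires the test, unless a further 4-weekly assessment was done during the hold. That assessment would itself be the second one.

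The remaining gap is a prompt stop, within 4 weeks of the draw that first showed the response.

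**5. Size, as an assumption.** Let L be the share of responders who would have been confirmed but have no second test. The observable ORR is p × (1 − L), and a false stage 1 stop has probability (1 − 0.20 × (1 − L))^12.

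| L (assumed) | Observable ORR when p = 0.20 | Power | False stage 1 stop | Level when p = 0.05 |
|---|---|---|---|---|
| 0 | 0.200 | 0.902 | 0.80^12 = 0.069 | 0.0935 |
| 5% | 0.190 | 0.882 | 0.81^12 = 0.080 | 0.081 |
| 10% | 0.180 | 0.857 | 0.82^12 = 0.092 | 0.070 |

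The level falls with L, so the error runs only towards a negative result.

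**The case against.** **The test is allowed.** A reader might infer that such a patient cannot be confirmed. The documents do not support that. Footnote c says when a test is required and forbids nothing, and sections 11.2.1 and 13.1 set no minimum interval. A voluntary repeat at the off-study visit would confirm the PR. This stands; the point is about a missing requirement.

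**Most toxicity pathways hold first.** General toxicities, rash, diarrhea, pneumonitis of grade 2 or 3, asymptomatic LVEF decline and the haematologic toxicities lead to discontinuation mainly after a hold of about 28 days or 4 weeks, by which time the test is usually required or a further assessment has been made. This also stands. It confines the gap to immediate stops, withdrawal and intercurrent illness soon after a first response.

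**The power statement is not wrong.** A reader might infer that the 90% holds only if every responder stays on treatment until the next test. Section 13.2 speaks of an extended ORR without a separate definition, and section 13.1 defines ORR as the confirmed rate. At a confirmed ORR of 20% the power is 0.902 as planned. The losses in the table arise only if 20% is taken as the rate that complete ascertainment would confirm.

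**No loss rate can be drawn from the documents.** It is tempting to use the AML/MDS study in section 2.2.1.2: "Twelve patients (23%) withdrew due to an AE, including cardiac failure (2) and infection (2"). It is a different disease, no exposure period is given, and the denominator is unclear: 12/0.23 is about 52 patients, while the same paragraph gives 45 for adverse events and 39 for efficacy. Many of those withdrawals could also fall outside the waiver. That figure is not used here.

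**One reading is not a response.** Confirmation exists to test a single reading, so some of these patients would have failed it anyway. That is fair, and it is why L counts only those who would have been confirmed.

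**Conclusion.** The gap is in the text and is narrow. A patient with a first PR or better who stops within 4 weeks of that assessment, for a reason other than progression, has no required second assessment. Without one, the patient is in the denominator of the confirmed ORR and not in the numerator.

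The direction is certain and conservative: a lower observed ORR and a higher chance of stopping a group wrongly at stage 1, with no inflation of the level. The size is not known. At assumed losses of 5% and 10%, power drops by 2.0 and 4.5 percentage points (0.902 to 0.882 and 0.857), and the false stage 1 stop rises by 1.1 and 2.3 points (0.069 to 0.080 and 0.092). The design in section 13.2 is correct as stated for its own endpoint. The change is worth making because one patient can decide stage 1 and the remedy is cheap.

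**What to change.** - **Footnote c, section 10.** Keep the 4-week waiver, except where the most recent assessment is an unconfirmed PR or better. In that case repeat the response-determining serum, urine or FLC test at the Off Study visit, before any new anti-myeloma therapy, whatever the date of the last tests.
- **Section 13.1.** State that this sample counts as the second consecutive assessment.
- **Section 11.2.2.** Reconcile the sentence on two consecutive assessments, which omits PR and includes PD, with section 13.1, which requires confirmation of PR, and section 11.2.1, which says that progression needs none.

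The repeat belongs at the Off Study visit. A sample at the 4-week safety visit would measure disease off drug, which is a different and debatable endpoint choice.

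The cost is a few sentences and a repeat laboratory test in a few patients, at a visit already marked for a myeloma assessment. Sample size, decision rules and treatment do not change. With every unconfirmed responder retested, none is lost for want of this test, and the design keeps its level of 0.0935 and power of 0.902.

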
## 11 MEASUREMENT OF EFFECT

### 11.1 Antitumor Effect – Solid Tumors N/A

### 11.2 Antitumor Effect – Hematologic Tumors

#### 11.2.1 Methods for Evaluation of Measurable Disease

**Measurable disease.** Measurable disease is defined as at least one of the following (these baseline laboratory studies for determining eligibility must be obtained within 28 days prior to enrollment):

1. Serum M-protein  $\geq 0.5$  g/dl ( $\geq 5$  g/l)
2. Urine M-protein  $\geq 200$  mg/24 h
3. Serum free light chains (FLC) assay: Involved FLC level  $\geq 10$  mg/dl ( $\geq 100$  mg/l) and an abnormal serum free light chain ratio ( $< 0.26$  or  $> 1.65$ )
4. Biopsy proven plasmacytoma (should be measured within 28 days of first study drug administration). Prior biopsy is acceptable.
5. If the serum protein electrophoresis is unreliable for routine M-protein measurement, quantitative immunoglobulin levels on nephelometry or turbidometry will be followed.

Patients will be evaluated under local Investigator review for disease response according to the International Myeloma Working Group (IMWG) uniform response criteria (see 11.2.2; Rajkumar 2011).

Tests Required To Assess Response (Must Be Done At Each Disease Measurement Visit)				
On Study Baseline Value	SPEP	24 hr UPEP	Ig FLC	Plasmacytoma assessment
Serum M-spike $\geq 0.5$ g/dl, and urine M-spike $\geq 200$ mg/24 hrs	X	X		
Serum M-spike $\geq 0.5$ g/dl, but urine M-spike $< 200$ mg/24 hrs	X			
Serum M-spike $< 0.5$ g/dl, and urine M-spike $\geq 200$ mg/24 hrs		X		
Serum M-spike $< 0.5$ g/dl, urine M-spike $< 200$ mg/24 hrs, but involved Ig FLC is $\geq 10$ mg/dL			X	
Plasmacytoma				X a
Immunofixation studies of both serum and urine are required to document CR regardless of registration values, and in addition FLC measurement and BM immunophenotyping is required to document sCR. a Complete evaluations done at baseline with same technique Q 12 weeks.				

Listed above are the minimal required tests to assess response based on the characteristics of disease at study initiation. All baseline evaluations should be performed as closely as possible to the beginning of treatment and never more than 4 weeks before the beginning of the treatment.

In order to be classified as a hematologic response, confirmation of serum monoclonal protein, serum immunoglobulin free light chain (when primary determinant of response) and urine monoclonal protein (when primary determinant of response) results must be made by verification on two consecutive determinations.

- Bone marrow aspirate and biopsy are **only** required to document or confirm CR or sCR, except for patients with evaluable disease **only**, where BM assessment is required to document all response categories including progression. However, a second confirmatory BM is **not** required to confirm response.
- Radiographic studies are not required to satisfy these response requirements, however, if radiographic studies were performed there should be no evidence of progressive or new bone lesions.
- Progression does not require confirmation, but treating physician may continue an additional cycle to confirm progression if clinically indicated.

Bone progression: Caution must be exercised to avoid rating progression or relapse on the basis of variation of radiologic technique alone. Compression fracture does not exclude continued response and may not indicate progression. When progression is based on skeletal disease alone, it should be discussed with the Principal Investigator before removing the patient from the study.

The same method of assessment and the same technique should be used to characterize each identified and reported lesion at baseline and during follow-up. Imaging-based evaluation is preferred to evaluation by clinical examination unless the lesion(s) being followed cannot be imaged but are assessable by clinical exam.

### 11.2.2 Response Criteria

International Myeloma Working Group Response Criteria (Rajkumar *et al.*, 2011)  
Response categories include sCR, CR, nCR, VGPR, PR, SD, and PD. In addition, minor response (MR) will be evaluated as an alternate response (see [Section 11.3](#) for definition).

Response	IMWG criteria
sCR	CR as defined below plus: 
 
• normal FLC ratio and
 
• absence of clonal cells in bone BM by immunohistochemistry or 2 – 4 color flow cytometry
 

CR	
 
• Negative immunofixation on the serum and urine and
 
• disappearance of any soft tissue plasmacytomas and
 
• < 5% plasma cells in BM.
 
• In patients with only FLC disease, a normal FLC ratio of 0.26–1.65 is required.
 

VGPR	
 
• Serum and urine M-protein detectable by immunofixation but not on electrophoresis or
 
• <math>\geq 90\%</math> reduction in serum M-protein plus urine M-protein level < 100 mg/24 h.
 
• In patients with only FLC disease, >90% decrease in the difference between involved and uninvolved FLC levels is required.
 

PR	
 
1. 50% reduction of serum M-protein and reduction in 24 hours urinary M-protein by <math>\geq 90\%</math> or to < 200 mg/24 h
 
 
 
• If the serum and urine M-protein are unmeasurable, a <math>\geq 50\%</math> decrease in the
 

	
difference between involved and uninvolved FLC levels is required in place of the M-protein criteria
 
 
• If serum and urine M-protein are not measurable, and serum free light assay is also not measurable, <math>\geq 50\%</math> reduction in plasma cells is required in place of M-protein, provided baseline BM plasma cell percentage was <math>\geq 30\%</math>
 
• In addition to the above listed criteria, if present at baseline, a <math>\geq 50\%</math> reduction in the size of soft tissue plasmacytomas is also required
 

Stable Disease	2. Not meeting criteria for CR, VGPR, PR or progressive disease
Progressive disease	
3. Increase of <math>\geq 25\%</math> from lowest response value in any one of the following:
 
 
1. Serum M-component (the absolute increase must be <math>\geq 0.5</math> g/dL) and/or
 
2. Urine M-component (the absolute increase must be <math>\geq 200</math> mg/24 h) and/or
 
3. Only in patients without measurable serum and urine M-protein, the difference between involved and uninvolved FLC levels. The absolute increase must be <math>> 10</math> mg/dL
 
4. Only in patients without measurable serum and urine M-protein and without measurable disease by FLC levels, bone marrow plasma cell percentage (absolute % must be <math>\geq 10\%</math>)
 
5. Definite development of new bone lesions or soft tissue plasmacytomas or definite increase in the size of existing bone lesions or soft tissue plasmacytomas
 
6. Development of hypercalcemia (corrected serum calcium <math>> 11.5</math> mg/dL) that can be attributed solely to the plasma cell proliferative disorder
 

All relapse categories (CR, sCR, VGPR, and PD) require two consecutive assessments made at any time before the institution of any new therapy; complete response and PR and SD categories also require no known evidence of progressive or new bone lesions if radiographic studies were performed. VGPR and CR categories require serum and urine studies regardless of whether disease at baseline was measurable in serum, urine both or either. Radiographic studies are not required to satisfy these response requirements. BM assessments need not be confirmed. For progressive disease, serum M-component increases of  $\geq 1$  gm/dl are sufficient to define response if starting M-component is  $\geq 5$  g/dl.

IMWG clarification for coding PD: Clarified that BM criteria for PD are to be used only in patients without measurable disease by M protein and by FLC levels. The 25% increase refers to M protein, FLC, and BM results, and does not refer to bone lesions, soft tissue plasmacytomas or hypercalcemia. Note the lowest response value does not need to be a confirmed value.

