### 11.3 Other Response Parameters

Additional response criteria for specific disease states:

Minor response in patients with relapsed and refractory myeloma adapted from the EMBT criteria 	$\geq 25\%$ but $< 49\%$ reduction of serum M protein and reduction in 24 hour urine M protein by 50 – 89%, which still exceeds 200 mg/24hrs.
---	--

	
In addition to above; if present at baseline, 25-49% reduction in the size of soft tissue plasmacytomas is also required
 
No increase in size or number of lytic bone lesions (development of compression fractures does not exclude response)

Immunophenotypic CR	Stringent CR plus Absence of phenotypic abarrent PC (clonal) in BM with a minimum of one million of total BM cells analyzed by miltiparamtric flow cytometry (with $\geq 4$ colors)
Molecular CR	Stringent CR plus negative ASO-PCR (sensitivity $10^{-5}$ )
Near Complete Response (adapted from the EMBT criteria  )	Patients, in whom all criteria for a CR are satisfied with exception of a positive or an unconfirmed immunofixation result, will be considered a near CR (nCR).

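### The VGPR definition has no plasmacytoma condition although CR, PR and MR do, so a patient whose plasmacytoma has shrunk by less than half can fail PR yet count as a responder in the primary ORR

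*Combined protocol and SAP*

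**What the plan says.** The response table in section 11.2.2, with section 11.3, treats soft tissue plasmacytomas as follows.

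- **CR:** "disappearance of any soft tissue plasmacytomas". sCR is built on CR, and near CR (11.3) needs every CR criterion except the immunofixation result, so both inherit the condition.
- **PR:** if a plasmacytoma was present at baseline, a ≥50% "reduction in the size of soft tissue plasmacytomas is also required".
- **Minor response (11.3):** if present at baseline, "25-49% reduction in the size of soft tissue plasmacytomas is also required".
- **Progressive disease:** a definite increase in an existing plasmacytoma, or a new one.
- **VGPR:** nothing. The first limb is "Serum and urine M-protein detectable by immunofixation but not on electrophoresis or". The second is a ≥90% "reduction in serum M-protein plus urine M-protein level" below 100 mg/24 h. A separate rule covers FLC-only disease.

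Stable disease is whatever meets none of CR, VGPR, PR or progression.

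Section 13.1 defines the primary ORR as confirmed PR or better, refers to the 11.2.2 definitions, and lists the qualifying statuses one by one, ending with "very good partial response or partial response noted as the objective status of two consecutive assessments". Biopsy-proven plasmacytoma is by itself sufficient as measurable disease (3.1.2 and 11.2.1).

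**The concern.** VGPR lies between CR and PR. Both neighbours carry a plasmacytoma condition and VGPR does not, so the scale is not ordered for a patient with soft tissue disease: the deeper category can be reached by someone who fails the shallower one.

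The immunofixation limb has a related gap, because it states no change from baseline. A patient enrolled on plasmacytoma alone, whose serum and urine M-protein are already visible only on immunofixation, could meet it with no change at all.

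VGPR feeds the primary ORR, the stage-1 gate (at least 1 of 12) and the final rule (at least 4 of 37) in each biomarker group. With cut-offs this low, one patient can change a decision. The same classification decides who has achieved less than a PR after 4 cycles, and so who may enter the secondary analysis of the combination. Response is judged by local investigators, so sites may read the row differently.

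**Working it through.** **Step 1. Apply the table as written.** Take a patient with measurable serum M-protein, urine M-protein below 100 mg/24 h, and a baseline plasmacytoma that is unchanged or has shrunk by less than 50%. Immunofixation remains positive. Serum protein is still visible on electrophoresis, and each result is confirmed on two consecutive assessments.

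| Category | Serum fall 89% | Serum fall 90% |
|---|---|---|
| CR, sCR, nCR | no (plasmacytoma present) | no (plasmacytoma present) |
| VGPR | no (below 90%) | **yes** |
| PR | no (plasmacytoma not halved) | no (plasmacytoma not halved) |
| MR | no (serum fall above the MR range) | no |
| PD | no (no definite growth) | no |
| Status | stable disease | VGPR |
| Primary ORR | non-responder | **responder** |

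The M-protein conditions for PR are met in both columns. Only the plasmacytoma clause separates the first column from PR, and that clause is absent from VGPR.

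**Step 2. Look for text that restores the condition.** Nothing in 11.2.1, 11.2.2, 11.3, 13.1 or 13.5.2 says that VGPR must also satisfy PR. The note under the response table says that VGPR needs both serum and urine studies whatever was measurable at baseline. That keeps VGPR open to plasmacytoma-only patients and does not mention the lesion.

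**Step 3. Reproduce the plan's design (13.2).** Inputs: n1 = 12, continue at ≥1 response; n = 37, accept at ≥4; null ORR 5%, alternative 20%; stated one-sided level 10% and power 90%.

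P(accept) = P(Bin(37, p) ≥ 4) − P(Bin(12, p) = 0) × P(Bin(25, p) ≥ 4)

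- p = 0.05: 0.1119 − 0.5404 × 0.0341 = 0.0935. Stage 2 opens with probability 1 − 0.95^12 = 0.460.
- p = 0.20: 0.9550 − 0.0687 × 0.7660 = 0.902.

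The design reproduces: 9.3% against the 10% level, and 90.2% power.

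**Step 4. Effect of one patient, given that it happens.** Suppose one of the 37 is counted only through this gap and the other 36 respond with probability 0.05.

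- Patient in stage 1: stage 2 is certain, and acceptance needs ≥3 of 36. 1 − (0.1578 + 0.2990 + 0.2753) = 0.268.
- Patient in stage 2: stage 1 must still produce a response. 0.2679 − 0.5404 × P(Bin(24, 0.05) ≥ 3) = 0.2679 − 0.5404 × 0.1159 = 0.205.

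**Step 5. Unconditional scale.** The documents give no plasmacytoma frequency, VGPR share or discordance rate, so every share below is assumed. Added ORR = 5% × VGPR share × plasmacytoma share × share with less than 50% shrinkage.

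| Assumed shares | Added ORR (points) | Expected patients per 37 | P(accept) |
|---|---|---|---|
| 1/3 × 10% × 50% | 0.08 | 0.03 | 9.8% |
| 1/2 × 20% × 50% | 0.25 | 0.09 | 10.7% |
| 1/2 × 30% × 100% | 0.75 | 0.28 | 13.6% |

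**The case against.** The strongest reply is that 13.1 speaks of PR or better, which suggests an ordered scale on which every VGPR is already a PR. That reading would close the gap, but it is nowhere stated, and 13.1 sends the reader to 11.2.2 and lists VGPR separately. At best the text is ambiguous on a primary-endpoint definition.

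Second, the table is presented as the cited IMWG criteria. A reader might infer a transcription error. The documents do not support that, because the source is not available here. The protocol's table governs the endpoint either way, but any edit is a departure from its wording and should be noted as such.

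Third, a reader might infer that plasmacytomas go unassessed, because the text says "Radiographic studies are not required to satisfy these response requirements". That goes too far. The tests table in 11.2.1 requires plasmacytoma assessment for these patients, every 12 weeks with the same technique, and the study calendar schedules extramedullary imaging at that interval. The lesion is measured; the VGPR row simply does not use the measurement.

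Fourth, a patient whose plasmacytoma grows is not credited with a response: definite growth is progression. The gap covers lesions that are unchanged or shrink by less than half.

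Fifth, a confirmed 90% M-protein fall is evidence of biological activity, so calling every such case an error is a judgment. That is fair for the 90% limb. It does not help the immunofixation limb, which can be met with no change. That case is narrow, however: read literally it needs both serum and urine positive on immunofixation, and for plasmacytoma disease the only minimum response test marked in 11.2.1 is the plasmacytoma assessment.

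**Conclusion.** The gap is real on the face of the text. It makes the primary endpoint discontinuous for patients with a baseline plasmacytoma: stable disease at a confirmed 89% fall, responder at a confirmed 90% fall, with the lesion unchanged or shrunk by less than half and urine M-protein below 100 mg/24 h. The immunofixation limb adds a second, narrower route.

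Its frequency cannot be found from the documents and is probably low. The figures of 26.8% and 20.5%, against 9.3%, are conditional on one such patient and a true ORR of 5% in the rest. They show how sensitive cut-offs of 1 and 4 are; they are not the trial's error rate. A reader might infer an error rate of 15% to 22%, which follows if the gap adds 1 to 2 points to ORR (15.1% at 6%, 21.9% at 7%). Nothing in the documents supports an addition that large: it equals one fifth to two fifths of the 5% null rate. The smaller assumed shares in the working give 9.8% to 13.6%.

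This is worth correcting because it concerns the primary endpoint and the correction is small. It does not undermine the design.

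**What to change.** 1. In the VGPR row of 11.2.2, add that the PR plasmacytoma condition (≥50% reduction if present at baseline) must also be met.
2. Limit the immunofixation limb of VGPR to patients whose M-protein was measurable on electrophoresis at baseline.
3. Optionally, state in 11.2.1 and 11.2.2 that the sentence on radiographic studies does not waive the plasmacytoma assessment in the 11.2.1 tests table. Do not word this in terms of bone surveys, which could imply surveys that are not now scheduled.
4. Record that the VGPR row departs from the wording of the cited table.

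Cost: a few lines of text. Sample size and decision rules stay as they are, and no test is added because plasmacytoma assessment every 12 weeks is already planned. ORR may be very slightly lower. A patient moved from VGPR to stable disease would also count as less than a PR for the option to add GSK2141795, so the sponsor should confirm that the edited definition and that provision agree. The change should be made before responses are classified for the stage-1 decision or, if that has passed, before the final analysis, with any affected patients listed.
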